### APPENDIX 1. PROGRAMMING CONVENTIONS FOR OUTPUTS

### OUTPUT CONVENTIONS

Outputs will be presented according to the following:

### **DATES & TIMES**

Depending on data available, dates and times will take the form dd-mmm-yyyy hh:mm:ss.

### **SPELLING FORMAT**

English UK

STATISTICAL ANALYSIS PLAN: PROTOCOL V56502 Page 34 of 40

### **PRESENTATION OF TREATMENT GROUPS**

For outputs, treatment groups will be represented as follows and in that order:

Treatment Group	For Tables and Graphs	For Listings (include if different to tables)
V565	V565	V565
Placebo	Placebo	Placebo

### **PRESENTATION OF VISITS**

For outputs, visits will be represented as follows as applicable in the tables and listings and in that order:

Long Name (default)
Screening
Baseline
Day 1
Day 14
Day 42/Early Termination
Day 42 (LOCF)
Day 42 (WOCF)
Day 56

### LISTINGS

All listings will be ordered by the following (unless otherwise indicated in the template):

- Treatment
- Subject ID
- date (where applicable),

### APPENDIX 2. **PARTIAL DATE CONVENTIONS**

Imputed dates will NOT be presented in the listings.

### ALGORITHM FOR TREATMENT EMERGENCE OF ADVERSE EVENTS:

START DATE	STOP DATE	ACTION
Known	Known	If start date < study drug start date, then not TEAE
		If start date >= study drug start date, then TEAE
	Partial	If start date < study drug start date, then not TEAE
		If start date >= study drug start date, then TEAE
	Missing	If start date < study drug start date, then not TEAE
		If start date >= study drug start date, then TEAE
Partial, but known components show that it cannot be on or after study med start date	Known	Not TEAE
	Partial	Not TEAE
	Missing	Not TEAE
Partial, could be on	Known	If stop date < study drug start date, then not TEAE
start date		If stop date >= study drug start date, then TEAE
	Partial	Impute stop date as latest possible date (i.e. last day of month if day unknown or 31st December if day and month are unknown), then:
		If stop date < study drug start date, then not TEAE
		If stop date >= study drug start date, then TEAE
	Missing	Assumed TEAE
Missing	Known	If stop date < study drug start date, then not TEAE

Page 36 of 40

START DATE	STOP DATE	ACTION
		If stop date >= study drug start date, then TEAE
	Partial	Impute stop date as latest possible date (i.e. last day of month if day unknown or 31st December if day and month are unknown), then:
		If stop date < study drug start date, then not TEAE
		If stop date >= study drug start date, then TEAE
	Missing	Assumed TEAE

Page 37 of 40

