### 8.2.5.1 Adverse Events

Treatment-emergent Adverse Event: A TEAE is defined as:

- A new event that occurs during or after treatment with study drug or
- Any event present at Baseline that worsens in either intensity or frequency after exposure to study drug.

Only TEAEs will be summarised.

The number and percentage of subjects experiencing TEAEs and serious TEAEs will be summarised by treatment group, and by MedDRA System Organ Class (SOC) and Preferred Term. The TEAEs will also be summarised by maximum severity and relationship to study medication in addition to SOC, Preferred Term and treatment group. Summaries will also be presented for serious TEAEs and for TEAEs leading to permanent discontinuation.

Medical history will be coded using the MedDRA latest version and listed for all subjects.

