### **17.1.** Adverse Events

Adverse Events (AEs) will be coded using MedDRA Version 19.1.

Treatment emergent adverse events (TEAEs) are defined as:

1. A new event that occurs during or after treatment with study drug or

2. Any event present at Baseline that worsens in either intensity or frequency after exposure to study drug.

Page 30 of 40

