### 17.1.1. ALL TEAEs

Incidence of TEAEs will be presented by System Organ Class (SOC) and Preferred Term (PT) and also broken down further by maximum severity and relationship to study drug.

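### SAP Appendix 2 classes any adverse event known to start before first dose as not treatment-emergent, with no test for worsening, against the definition in SAP 17.1

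*SAP*

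**What the plan says.** The definition has two limbs. In SAP 17.1 the first reads "A new event that occurs during or after treatment with study drug or" and the second "Any event present at Baseline that worsens in either intensity or frequency after exposure to study drug". Protocol 6.2.1 and 8.2.5.1 give the same two limbs.

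TEAE status decides what is tabulated. Protocol 8.2.5.1 states "Only TEAEs will be summarised". SAP 17.1.1 says "Incidence of TEAEs will be presented by System Organ Class (SOC) and Preferred Term (PT"), with further breakdowns by maximum severity and relationship. SAP 17.1.2 to 17.1.4 restrict the discontinuation, serious and fatal summaries to TEAEs as well.

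SAP Appendix 2, titled "PARTIAL DATE CONVENTIONS", contains the algorithm for treatment emergence:

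- **Known start date:** each of the three stop-date rows says "If start date < study drug start date, then not TEAE".
- **Start date described as** "Partial, but known components show that it cannot be on or after study med start date": all three stop-date rows return not TEAE.
- **Start date missing, or partial and possibly on or after first dose:** the rule is "If stop date >= study drug start date, then TEAE" for a known or imputed stop date. A missing stop date is presumed to be a TEAE.

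**The concern.** The algorithm decides on dates alone. No row looks at severity or frequency, so for an event whose start is known or certain to precede first dose the second limb of the definition can never be met. A programmer who follows Appendix 2 gets a different answer from one who follows section 17.1.

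Such events can arise. AEs are recorded from consent (Protocol 6.2.1.2), screening lasts up to 28 days, and an AE that begins in screening may still be ongoing at first dose. Safety and tolerability is a secondary objective (SAP 2.2), no data monitoring committee is planned (SAP 4.1), and no between-group safety tests are planned (SAP 17). The descriptive TEAE tables are therefore the main summary of adverse events, and a worsening event left out of them can be found only in the listings.

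**Working it through.** The plan states no figure on this point, so there is none to reproduce. The check sets the algorithm against the definition.

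**Step 1: the test case.** Take an AE with true onset before first dose, still ongoing at first dose, that increases in intensity or frequency on study drug and is held under one record with its original start date. Its stop date, where known or imputed as the latest possible date, is on or after first dose. Under SAP 17.1 it is a TEAE.

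**Step 2: run it through Appendix 2.** There are 4 start-date states and 3 stop-date states (known, partial, missing), so 4 × 3 = 12 cells.

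| Start date | Cells | Appendix 2 | SAP 17.1 |
|---|---|---|---|
| Known, before first dose | 3 | not TEAE | TEAE |
| Partial, certainly before first dose | 3 | not TEAE | TEAE |
| Partial, could be on or after first dose | 3 | TEAE | TEAE |
| Missing | 3 | TEAE | TEAE |

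The two disagree in 3 + 3 = 6 of 12 cells. In the other 6 they agree, but only because the algorithm presumes emergence from the stop date. It would give the same answer had the event not worsened. So a fully dated event that worsened is left out, while an undated event that was merely ongoing is counted.

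**Step 3: does the case depend on recording?** Yes. Protocol 6.2.1 treats an exacerbation, or a rise in intensity or frequency, of a pre-existing condition as an AE. Protocol 6.2.1.2 asks for separate entry of each event. Neither says whether worsening of an AE already on file is a separate event, or which start date it takes.

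- If the worsening is entered as a new record dated at the worsening, its start is after first dose and Appendix 2 returns TEAE.
- If the original record is kept and updated, Appendix 2 returns not TEAE.

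**Step 4: which outputs are affected?** The AE tables: incidence, maximum severity, relationship, serious, discontinuation and fatal TEAEs. Laboratory, vital sign, ECG and physical examination summaries do not use TEAE status. Protocol 8.2.5 puts all safety data in by-subject listings, so the event stays visible there.

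**Step 5: after the change.** With a worsening test ahead of the date test, the 6 discordant cells become TEAE, so 6 + 6 = 12 of 12 agree with SAP 17.1.

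**The case against.** The strongest reply is that Appendix 2 is a convention for incomplete dates. SAP 7.3 cites it for imputing missing dates, section 17.1 holds the operative definition, and nothing says that the appendix overrides it. The events at risk are also few in kind. Under Protocol 6.2.1, conditions present before consent are medical history, and symptoms of the disease under study are not AEs unless worse or more frequent than expected. Many Crohn's symptoms would therefore first become an AE when they worsen on drug, and an onset entered at that point gives TEAE. Sites may also enter a worsening as a new record. Finally, the SAP contents list subsections on severity and relationship whose text is absent from the public version, so a linking rule there cannot be excluded.

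Most of this stands, and it narrows the point. It does not remove it. The algorithm has rows for fully known start and stop dates, so it classifies complete records too, and no visible text says that 17.1 prevails.

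Three stronger readings are tempting, and the documents do not support them:

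- **That every AE starting before first dose is lost.** Events with a missing or ambiguous start date become TEAEs when the stop date is missing or on or after first dose.
- **That all safety tables are affected.** Only the AE summaries depend on TEAE status.
- **That the drug will look safer than it is.** The rule applies to both arms and the ambiguous-date rows lean towards over-counting. A difference between arms would be understated only if worsening were more frequent on V565.

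**Conclusion.** Wrong as written: a stated classification rule contradicts the plan's own definition, and gives the wrong answer when followed, for AEs whose start is known or certain to precede first dose and which then worsen on drug.

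The practical loss is confined to AEs that arise in the screening window of at most 28 days, are ongoing at first dose, worsen on drug and stay under their original record. The number of subjects cannot be computed. The documents give no rate for ongoing AEs at first dose or for worsening, and any count would rest on assumed values for both. The conclusion assumes that Appendix 2 is applied as printed and that no text missing from the public SAP links it to section 17.1.

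**What to change.** In the six affected rows of Appendix 2 (three with a known earlier start, three with a partial start that is certainly earlier), change the action to: not TEAE, unless intensity or frequency increases on or after first dose; then TEAE, with onset at the date of worsening. Add a sentence that section 17.1 governs Appendix 2. The condition should stop at intensity or frequency, because neither definition mentions seriousness.

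Equivalently, state in the data-entry instructions that post-dose worsening of an AE already recorded is entered as a new record dated at the worsening. The algorithm then works unchanged, so only one of the two routes is needed.

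The cost is a few lines of SAP text and minor programming, or one line of entry guidance. The TEAE count may rise slightly.

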### ALGORITHM FOR PRIOR / CONCOMITANT DRUGS:

START DATE	STOP DATE	ACTION
Known	Known	If stop date < study drug start date, assign as prior If stop date >= study drug start date and start date <= end of treatment, assign as concomitant If stop date >= study drug start date and start date > end of treatment, assign as post study
	Partial	Impute stop date as latest possible date (i.e. last day of month if day unknown or 31 st December if day and month are unknown), then: If stop date < study drug start date, assign as prior If stop date >= study drug start date and start date <= end of treatment, assign as concomitant If stop date >= study drug start date and start date > end of treatment, assign as post treatment
	Missing	If stop date is missing could never be assumed a prior drug If start date <= end of treatment, assign as concomitant If start date > end of treatment, assign as post treatment
Partial	Known	Impute start date as earliest possible date (i.e. first day of month if day unknown or 1 st January if day and month are unknown), then: If stop date < study drug start date, assign as prior If stop date >= study drug start date and start date <= end of treatment, assign as concomitant If stop date >= study drug start date and start date > end of treatment, assign as post treatment
	Partial	Impute start date as earliest possible date (i.e. first day of month if day unknown or 1 st January if day and month are unknown) and impute stop date as latest possible date (i.e. last day of month if day unknown or 31 st December if day and month are unknown), then: If stop date < study drug start date, assign as prior If stop date >= study drug start date and start date <= end of treatment, assign as concomitant If stop date >= study drug start date and start date > end of treatment, assign as post treatment

Page 38 of 40

START DATE	STOP DATE	ACTION
	Missing	Impute start date as earliest possible date (i.e. first day of month if day unknown or 1 st January if day and month are unknown), then: If stop date is missing could never be assumed a prior drug If start date <= end of treatment, assign as concomitant If start date > end of treatment, assign as post treatment
Missing	Known	If stop date < study drug start date, assign as prior If stop date >= study drug start date, assign as concomitant Cannot be assigned as 'post treatment'
	Partial	Impute stop date as latest possible date (i.e. last day of month if day unknown or 31 st December if day and month are unknown), then: If stop date < study drug start date, assign as prior If stop date >= study drug start date, assign as concomitant Cannot be assigned as 'post treatment'
	Missing	Assign as concomitant

Page 39 of 40

Page 40 of 40
